3.2. Study Endpoints

The efficacy, safety, and exploratory objectives and corresponding endpoints are presented in Table 1 below.

Table 1: Study Endpoints

Objectives	Endpoints
Primary Efficacy	
To compare the efficacy of zetomipzomib with that of placebo in patients with active Class III/IV +/-V LN on background MMF (or equivalent) and corticosteroids based upon current guideline-driven standard of care	Proportion of patients achieving CRR at Week 37
Secondary Efficacy	
To compare the efficacy of zetomipzomib	Key Secondary:
with that of placebo in patients with active Class III/IV +/-V LN on background MMF (or	Proportion of patients achieving PRR at Week 37
equivalent) and corticosteroids based upon	Proportion of patients achieving CRR at Week 53
current guideline-driven standard of care	Proportion of patients achieving PRR at Week 53
	Proportion of patients achieving CRR at Week 25
	Proportion of patients achieving PRR at Week 25
	Other Secondary:
	Percentage change from Baseline in UPCR by visit
	Time to CRR
	Time to PRR
	• Time to UPCR ≤ 0.5
	Time to death or renal-related events
	• Proportion of patients achieving CRR (at Weeks 25, 37, and 53) with successful taper of prednisone or equivalent to ≤5 mg by Week 17
	• Proportion of patients achieving CRR (at Weeks 25, 37, and 53) with no use of prednisone or equivalent during the 8 weeks prior to the renal response assessment
	• Proportion of patients with UPCR ≤0.5 at Weeks 13, 25, 37, and 53
	• Proportion of patients achieving CRR with UPCR ≤ ULN at Weeks 25, 37, and 53
	Change from Baseline in clinical SLEDAI-2K score, excluding complement and anti-dsDNA components
	Change from Baseline in EuroQol 5-Dimension 5-Level (EQ-5D-5L)

Objectives	Endpoints
Safety	
To determine the safety and tolerability of zetomipzomib in patients with active LN on background standard of care, MMF or equivalent, and corticosteroids.	 Incidence and severity of TEAEs Clinical laboratory tests (hematology, serum chemistry, urinalysis, coagulation, other) Vital sign measurements (height/weight, body mass index, body temperature, systolic blood pressure, diastolic blood pressure, heart rate, and respiratory rate) Physical examination 12-lead ECG assessments
Exploratory Efficacy	
 To evaluate the speed of action of zetomipzomib compared with placebo To evaluate the clinical benefit of zetomipzomib compared with placebo To evaluate changes in serum levels of selected parameters in zetomipzomib compared with placebo To evaluate the efficacy of zetomipzomib compared with placebo on clinical lupus disease assessments To evaluate the efficacy of zetomipzomib compared with placebo on improving patient's quality of life To evaluate relapse in zetomipzomib compared with placebo To evaluate glucocorticoid-related AEs in zetomipzomib compared with placebo To evaluate renal histopathology and immunohistopathology (at selected sites based on feasibility) To evaluate the pharmacokinetics of zetomipzomib 	 Proportion of patients achieving PRR with successful taper of prednisone or equivalent to ≤5 mg by Week 17 Proportion of patients achieving PRR with no use of prednisone or equivalent during the 8 weeks prior to the renal response assessment Proportion of patients who develop doubling of Baseline serum creatinine, kidney failure (receiving dialysis or kidney transplantation), or death Change from Baseline in antibodies (anti-dsDNA antibody, C1q autoantibody) and time to antibodies normalization or negative status (anti-dsDNA antibody normalization, anti-C1q antibody negative status) Change from Baseline in complement (C3, C4) and time to complement (C3, C4) normalization status Change from Baseline in serum albumin Change from Baseline in serum albumin Change from Baseline in serum lipids (serum LDL cholesterol, serum total cholesterol, serum triglycerides) Change from Baseline in blood HbA1c Change from baseline in the GTI as measured by the GTI-CWS and the GTI-AIS Proportion of patients with Baseline SLEDAI-2K, excluding renal components, ≥6 with at least a 4-point improvement

Objectives Endpoints	
	Change from Baseline in SLEDAI-2K
	• Change from Baseline in 28-joint counts
	Change from Baseline in PGA score
	• Proportion of patients with relapse or proteinuric flare
	Time to relapse or proteinuric flare
	Proportion of patients with SLE Flare Index of severe, moderate, or mild
	Time to SLE Flare Index of severe, moderate, or mild
	• Time to antibodies normalization or negative status (anti-dsDNA antibody normalization, anti-C1q antibody negative status)
	• Time to complement (C3, C4) no longer being low
	• Change from Baseline in IgM, IgG, and IgA
	 Change from Baseline in renal biopsy histopathology and immunohistopathology (optional)*
	 Pharmacogenomics profile (RNA sequencing) and biomarkers*
	Pharmacokinetics profile*

^{*} Endpoint is outside the scope of this SAP. anti-dsDNA=anti-double stranded DNA; C1q=C1q Autoantibody; CRR=complete renal response; C3=Complement Component 3; C4=Complement Component 4; DNA=deoxyribonucleic acid; ECG=electrocardiogram; eGFR=estimated glomerular filtration rate; EQ-5D-5L=EuroQol 5-Dimension 5-Level; GTI=Glucocorticoid Toxicity Index; GTI-CWS=GTI Cumulative Worsening Score; GTI-AIS=GTI Aggregate Improvement Score; HbA1c=hemoglobin A1c; LDL=low-density lipoprotein; LN=Lupus Nephritis; MMF=Mycophenolate Mofetil; PGA=physician global assessment; PRR=partial renal response; RNA=ribonucleic acid; SLE=Systemic Lupus Erythematosus; SLEDAI-2K=Systemic Lupus Erythematosus Disease Activity Index 2000; TEAE=Treatment-Emergent Adverse Event; ULN=upper limit of normal; UPCR=urine protein to creatinine ratio.

3.2.1. Definitions Related to Study Endpoints

Baseline values for 24-hour UPCR and all other endpoints are defined in Section 4. See Section 8 for additional information related to the efficacy endpoints.

3.2.1.1. Complete renal response (CRR)

- A UPCR ≤0.5 in one 24-hour urine sample (for Weeks 13, 25, 37 [primary endpoint], and 53)
- An estimated glomerular filtration rate (eGFR) ≥60 mL/min/1.73 m² or no confirmed decrease of >20% from Baseline eGFR.
- For primary endpoint at Week 37, CRR must be adjudicated by CEC

3.2.1.1.1. Calculations Associated with CRR

UPCR is the ratio of urine protein to urine creatinine in the 24-hour urine sample, where urine protein and urine creatinine are expressed in the same units.

eGFR is calculated based on the following Chronic Kidney Disease Epidemiology Collaboration formula (Inker et al., 2021).

eGFR = $142 \times \text{min}(\text{standardized } S_{cr}/\kappa, 1)^{\alpha} \times \text{max}(\text{standardized } S_{cr}/\kappa, 1)^{-1.200} \times 0.9938^{Age} \times 1.012 \text{ [if female], where:}$

- S_{cr} is serum creatinine in mg/dL
- κ is 0.7 for females and 0.9 for males
- α is -0.241 for females and -0.302 for males
- min indicates the minimum of S_{cr}/κ or 1
- max indicates the maximum of S_{cr}/κ or 1

3.2.1.2. Partial renal response (PRR)

• A \geq 50% reduction of UPCR from Baseline, and to <1.0 if the Baseline UPCR was <3.0 or to <3.0 if the Baseline value was \geq 3.0.

3.2.1.3. Time-to-event endpoints

When calculating the time-to-CRR or time-to-PRR endpoints, all timepoints where UPCR data is collected will be considered. The UPCR criteria for CRR/PRR may be met using the 24-hour urine tests for Weeks 13, 25, 37, and 53. For all other timepoints, UPCR criteria for CRR/PRR will use 2 consecutive first morning void (FMV) urine tests.

When calculating time-to-FMV-CRR and time-to-FMV-PRR endpoints, if the 24-hour urine test is not available, then 2 consecutive FMV urine tests may be used at Weeks 13, 25, 37, and 53. For all other timepoints, UPCR criteria for CRR/PRR will use FMV urine tests.

Any time the 24-hour urine test is available and valid it should be used for analysis over the FMV urine test (Weeks 13, 25, 37, and 53).

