## 7.2.2.2. Proteinuria Evaluation

Proteinuria will be evaluated via spot UPCR (first morning void) and 24-hour urine collection.

At Screening, patients will be instructed to collect two 24-hour urine collection samples, at least 7 days apart. Both samples must demonstrate UPCR levels meeting protocol inclusion criteria in order to be eligible. If 1 of these samples fails to demonstrate UPCR levels meeting protocol inclusion criteria, then an additional 24-hour urine collection sample may be obtained at least 7 days from the last sample taken. At least one 24-hour urine collection should be within 14 days

of randomization; an additional 7 days (up to 21 days total) may be permitted if approved by the Medical Monitor or the Sponsor. In addition, a first morning void sample will also be collected at these same time points for a spot UPCR.

Baseline UPCR will be determined by the average of the 24-hour collections at Screening.

Once enrolled, 24-hour urine samples will be collected according to the Schedule of Assessments (Appendix 3). Patients should be instructed to return the chilled 24-hour urine sample to the site following its collection, which should occur during the 48 hours prior to the visit. A first morning void sample should also be collected at these same time points for a spot UPCR.

After Day 1 (Week 1), the 24-hour urine collection sample will be used to assess UPCR level at the specified visits. If the clinical laboratory test results indicate that a urine collection sample is inadequate at any time point, then the spot UPCR obtained from the first morning void sample may be used instead for assessments performed after Day 1 (Week 1).

The 24-hour urine collection sample may be postponed up to 14 days at the discretion of the Investigator if menstrual bleeding or a genitourinary tract infection is present at time of urinallysis or anytime during the collection.

In the case that any 24-hour urine collection is missed after randomization, it is suggested to collect a replacement 24-hour urine within 4 weeks from the missed collection date.

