#### Baseline value:

Baseline UPCR will be determined by the average of the 24-hour collections at Screening.

Unless specified otherwise, baseline value for eGFR and other parameters including laboratory data is defined as the last value prior to the 1st dose of the zetomipzomib or placebo.

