Continuous efficacy endpoints (ie, change or percentage change from Baseline in UPCR by visit) will be analyzed using the longitudinal data analysis method based on a mixed model for repeated measures (MMRM) approach. This model will include fixed effect terms for randomized treatment, timepoint (ie, visit) and randomized treatment by timepoint interaction. Within subject error will be modelled by use of an unstructured variance-covariance matrix. Baseline value will be included as a covariate and the randomization stratification factors will be included as class terms. Treatment effect (ie, the difference in least-square mean values between

each zetomipzomib dose and placebo and the 2 zetomipzomib doses combined vs placebo) estimates will be extracted from the model by timepoint along with the associated 95% CIs and 2-sided p-values. A sensitivity analysis of this model by using multiple imputation (MI) for handling missing data will be performed. The influence of missing data over time will be assessed using multiple imputation techniques, specifically assuming missing at random and missing not at random (MNAR); for the latter both jump to placebo and tipping point MI analyses will be employed.

The Baseline value for 24-hour UPCR is defined as the average of non-missing 24-hour UPCR results from the Screening visit. Repeat test results will not be used to replace non-missing original test data. When only 1 non-missing sample 24-hour UPCR results from the Screening visit is available, then that single value will be used for the Baseline. Unless specified otherwise, baseline value for eGFR and other parameters including laboratory data is defined as the last value prior to the 1st dose of zetomipzomib or placebo.

In this study, all analyses involving treatment comparisons will be performed based on pairwise comparisons for zetomipzomib 60 mg versus the pooled placebo group and for zetomipzomib 30 mg versus the pooled placebo group. No statistical comparisons will be performed between the 2 zetomipzomib dose groups.

All analyses will be performed in SAS® v9.4 for Microsoft® Windows®.

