4. GENERAL STATISTICAL CONSIDERATIONS

This section presents general rules for the derivation and reporting of study data. If a subsequent section related to a specific derivation or analysis differs from this general guidance, the subsequent section takes precedence.

Unless specified otherwise, all study data will be summarized using descriptive statistics. Descriptive statistics for continuous data include number of patients (n), mean, standard deviation (SD), median, quartiles, minimum, and maximum. Categorical data will be described using frequency counts and percentages in each category.

Mean, median, and quartiles will be displayed to one level of precision greater than the data as originally collected. Standard deviation will be displayed to two levels of precision greater than the original data. For the summary statistics of all numerical variables, unless otherwise specified, minimum and maximum will be displayed to the same level of precision as the original data.

When count data are presented, the percentage will be suppressed when the count is zero to draw attention to the non-zero counts. A row denoted "Missing" will be included in count tabulations where specified on the shells to account for missing values. Unless otherwise specified, the denominator for all percentages will be the number of patients in that treatment group within the analysis set of interest. Percentages will be presented to one decimal place except for the display of 100% frequency which will be displayed as 'XX (100)'.

P-values ≥0.001 will be presented to 4 decimal places as "0.xxxx". P-values <0.001 will be presented as "<0.001". P-values >0.999 will be presented as ">0.999". Confidence intervals (CIs) will be displayed to one level of precision greater than the data as collected.

Treatment groups will be labeled as "Zetomipzomib 60 mg", "Zetomipzomib 30 mg", and "Placebo". In general, all tables and figures will be presented by treatment group. All study data will be presented in by-patient data listings sorted by treatment group, patient ID, and assessment date/time.

"No patients qualify for this table" will be presented when there are no data available to report in a given table. A similar note will be presented for empty listings and figures.

For all other parameters, the baseline value will be defined as the last non-missing evaluation prior to the first dose of study treatment (zetomipzomib or placebo), unless otherwise specified.

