8.4.1. Analysis of Continuous Secondary Efficacy Endpoints

Continuous secondary efficacy endpoints include:

- Percentage change from Baseline in UPCR by visit
- Change from Baseline in clinical Systemic Lupus Erythematosus Disease Activity Index 2000 (SLEDAI-2K) score, excluding complement and anti-dsDNA components
- Change from Baseline in EuroQol 5-Dimension 5-Level (EQ-5D-5L) index score and EQ-VAS of general health.

Observed values of the continuous secondary efficacy endpoints will be analyzed using the longitudinal data analysis method based on a mixed model for repeated measures (MMRM) approach. The model will include fixed effect terms for randomized treatment, visit, and randomized treatment by timepoint interaction. Baseline value will be included as a covariate and the randomization stratification factors will be included as class terms. Within subject error will be modeled by use of an unstructured variance-covariance matrix. If the model does not converge using the unstructured matrix (TYPE=UN), the following variance-covariance structures will be tried in this order until convergence is achieved: Toeplitz (TYPE=TOEP), compound symmetric (TYPE=CS).

Treatment effect (ie, the difference in least-square mean values between each zetomipzomib dose vs pooled placebo and the 2 zetomipzomib doses combined vs pooled placebo) estimates will be extracted from the model by visit along with the associated 95% CIs and 2-sided p-values.

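### Time to PRR applies a 50% fall to first-morning-void samples, but the only UPCR baseline the Protocol names is the 24-hour average, so the criterion depends on the urine method

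*SAP*

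**What the plan says.** Baseline. Protocol 7.2.2.2 and 10.1 define one UPCR baseline, without qualification: "Baseline UPCR will be determined by the average of the 24-hour collections at Screening". Protocol 10.6 repeats the rule for the 24-hour measure: "The Baseline value for 24-hour UPCR is defined as the average of non-missing 24-hour UPCR results from the Screening visit".

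Criterion. SAP 3.2.1.2 asks for a fall of at least 50% plus an absolute cut that depends on where the patient started: "reduction of UPCR from Baseline, and to <1.0 if the Baseline UPCR was <3.0 or to <3.0 if the Baseline value was" 3.0 or higher.

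Specimen. For time to CRR and time to PRR, SAP 3.2.1.3 uses the 24-hour test at Weeks 13, 25, 37 and 53. Elsewhere, "For all other timepoints, UPCR criteria for CRR/PRR will use 2 consecutive first morning void (FMV) urine tests". The same section defines time to FMV-PRR, which relies on FMV at the other visits and also lets two FMV tests stand in for an unavailable 24-hour test. SAP 8.2.3.4 re-derives missing CRR and PRR from two FMV samples as a sensitivity analysis. Neither section states a baseline for the FMV values.

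Available data. Protocol 7.2.2.2 says of the Screening 24-hour collections: "In addition, a first morning void sample will also be collected at these same time points for a spot UPCR". The schedule of assessments also marks FMV at Screening. Neither document expressly gives those samples a role as a baseline.

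Percentage change. SAP 8.4.1 lists "Percentage change from Baseline in UPCR by visit" without naming the specimen or the visits.

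**The concern.** A criterion stated as a percentage fall means the same thing at every visit only if numerator and baseline come from the same kind of sample, or if the two methods agree on average. If FMV reads systematically lower than 24-hour urine, part of the apparent fall at an FMV visit is the change of method, and PRR is credited early. If it reads higher, PRR is credited late. Requiring two consecutive FMV tests reduces random error, but both tests carry the same systematic offset.

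By the schedule, 9 of the 13 urine visits from Week 5 to Week 53 are FMV-only, so this is the usual case for time to PRR. Time to PRR is a listed secondary endpoint, and speed of action is a stated exploratory objective (SAP Section 2). Both depend on when the threshold is crossed.

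**Working it through.** **The plan's own figures.** The documents give no number on FMV/24-hour agreement, so there is none to reproduce on this point. The sample-size statement (83 per group, 40% versus 20%, 2-sided 0.05) reproduces at 80.9% power with a pooled variance, against a stated 80%. It concerns CRR at Week 37 and does not depend on this issue.

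**Inputs.** B is the 24-hour baseline UPCR (Protocol 10.1). The 50% fall and the absolute cuts come from SAP 3.2.1.2. r is FMV UPCR divided by 24-hour UPCR in the same patient at the same time. r is not in the documents; the range 0.7 to 1.3 is an assumption for illustration.

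**Where the 50% rule binds.** PRR at an FMV visit needs FMV ≤ 0.5B and also FMV below the cut.
- B below 3.0 (cut 1.0): 0.5B is at or below 1.0 when B ≤ 2.0. Entry requires at least 1.0 for Class III/IV, so the 50% rule binds from 1.0 to 2.0.
- B of 3.0 or more (cut 3.0): 0.5B is at or below 3.0 when B ≤ 6.0, so the 50% rule binds from 3.0 to 6.0.
- Between 2.0 and 3.0, and above 6.0, the absolute cut is the stricter condition and the formula below is not the operative threshold.

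**True fall needed with a 24-hour baseline.** FMV = r × (24-hour value). The condition r × (24-hour value) ≤ 0.5B gives 24-hour value ≤ (0.5/r) × B, so the true fall needed is 1 - 0.5/r. An unchanged patient shows an apparent fall of 1 - r.

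| Assumed r | True fall needed, 1 - 0.5/r | Apparent fall if nothing changed, 1 - r |
|---|---|---|
| 0.7 | 28.6% | 30% |
| 0.8 | 37.5% | 20% |
| 0.9 | 44.4% | 10% |
| 1.0 | 50.0% | 0% |
| 1.1 | 54.5% | -10% |
| 1.2 | 58.3% | -20% |
| 1.3 | 61.5% | -30% |

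**With an FMV baseline.** The baseline is rB, so the condition is r × (24-hour value) ≤ 0.5 × rB. r cancels if it is constant within the patient, and the true fall needed is 50% at every visit.

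**Example.** B = 1.6 and r = 0.8. Against the 24-hour baseline, PRR needs FMV ≤ 0.8, which is a 24-hour value of 0.8/0.8 = 1.0, a true fall of 0.6/1.6 = 37.5%. Against an FMV baseline of 0.8 × 1.6 = 1.28, it needs FMV ≤ 0.64, a 24-hour value of 0.64/0.8 = 0.8, a true fall of 50%.

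**The case against.** The best counter-argument is that a like-for-like baseline may already be implied. Protocol 10.6 ties the averaging rule to the 24-hour measure, and SAP Section 4 has a default: "For all other parameters, the baseline value will be defined as the last non-missing evaluation prior to the first dose of study treatment". SAP Appendix 12 lists FMV UPCR as a separate analyte, so FMV UPCR could fall under that default. The SAP wording on the 24-hour baseline that seems to come before this sentence is not in the public text, and nothing is held against the plan for that. This reading is possible, but no section connects it to PRR. It also yields the last single pre-dose FMV value rather than an average, so two programmers could derive different PRR dates from the same data.

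Two further points stand. The formula does not describe PRR where the absolute cuts bind. And time to PRR is an other secondary endpoint, reported with nominal p-values (SAP 8.1).

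A reader might go further and infer that percentage change in UPCR at FMV visits is measured against the 24-hour baseline, so that the by-visit curve moves up and down with the method. The documents do not say so. SAP 8.4.1 leaves specimen and visits open, and the SAP's one definition of the ratio, given under the CRR calculations, is: "UPCR is the ratio of urine protein to urine creatinine in the 24-hour urine sample". If that applies throughout, percentage change is 24-hour against 24-hour.

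**Conclusion.** The point holds for time to PRR, time to FMV-PRR and PRR in the FMV-substitution analysis. Read plainly, these judge FMV values against a 24-hour baseline, so the 50% criterion means 50% only if r = 1. For baselines of 1.0 to 2.0 and 3.0 to 6.0, the true fall needed would be 37.5% at r = 0.8 and 58.3% at r = 1.2. Those ratios are assumptions; the documents support neither a size nor a direction.

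Two stronger conclusions do not follow. First, the primary endpoint and the main analyses of key secondary PRR at Weeks 25, 37 and 53 are not affected: the footnote to SAP Table 3 requires the 24-hour sample at those visits and rules out FMV, so they compare 24-hour with 24-hour. Second, nothing shows that the treatment difference is compressed or biased. The rule is the same in all arms, and moving a threshold equally in each arm can widen or narrow a difference depending on the response distributions. The consequence is for the timing and interpretation of response. For percentage change in UPCR, the finding is an open specification only.

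**What to change.** In SAP 3.2.1.2, 3.2.1.3 and 8.2.3.4, compute the percentage reduction by method: FMV values against the mean Screening FMV UPCR, and 24-hour values against the 24-hour baseline. Keep the 24-hour baseline for assigning patients to the below-3.0 or 3.0-and-above category.

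In SAP 8.4.1, specify that percentage change in UPCR uses 24-hour values against the 24-hour baseline. If FMV visits are analysed as well, use the FMV baseline for them and do not mix the two methods in one series.

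The cost is SAP wording and one extra derived baseline from samples already collected; sample size and power do not change. One limit remains: the absolute cuts (0.5, 1.0 and 3.0) still depend on the method. An FMV value of 1.0 corresponds to a 24-hour value of 1.0/r, which is 1.25 at r = 0.8 and 0.83 at r = 1.2. The change makes the 50% part of PRR consistent across visits, not the whole definition.
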